8.2.7. Investigational Product Adherence

[figure not shown]
IP adherence (%) is defined as the number of tablets taken, divided by the number of tablets planned to be taken, times 100. Number of tablets planned to be taken will be derived using an algorithm identical to that used for the derivation of planned exposure, but with the assigned dose replaced with the number of assigned tablets (15 mg = 1 tablet per day, 30 mg = 2 tablets per day, 45 mg = 3 tablets per day, 60 mg = 4 tablets per day).

Total tablets taken and IP adherence will be summarized descriptively using the Safety Set. Number and percentage of participants with IP adherence in categories <75%, 75 to 100%, >100% will be provided.

A large black rectangular redaction box covers the majority of the page content, from approximately y=150 to y=950. In the top left corner, there are four smaller black rectangular redaction boxes: one at the top left, one below it, one to its right, and one below that one. The rest of the page is white.

8.4. Safety Analysis

Safety and tolerability of SAGE-324 will be assessed based on TEAEs, changes from baseline in clinical laboratory evaluations, 12-lead ECGs, and vital signs, C-SSRS, PWC-20, and ESS. Safety data will be listed by participant.

For safety summary tables, the safety endpoints evaluated at scheduled visits are taken as done and nominal visit will be summarized as scheduled visits. For multiple values from the specific visit window, the choice of the visit record will be following the same rule as described in [Section 8.3.2](#).

All safety summaries will be prepared by dose level and overall for the Safety Set. See [Table 4](#) for details on how safety endpoints will be presented.

Table 4: Presentation of Safety Endpoints

Safety Evaluation	Incidence	Raw Value	Change from Baseline	Abnormality	Derived PCS values
TEAEs	X	*			
Vital Signs		X, *	X		X, *
12-lead ECG		X, *	X	X, *	X, * (QTcF only)
Safety Labs (Chemistry, Hematology, Urinalysis)		X, *	X	X, *	X, *
ESS	X	*	X		
PWC-20	X	*			
C-SSRS	X	*	X		

X = Safety Assessment will be summarized in tables
 * = Safety Assessment will be presented in individual participant data listings
 Note: PCS = Potentially Clinically Significant.

8.4.1. Adverse Events

Adverse events will be coded using MedDRA Version 25 or higher. In the event of a missing/incomplete start or stop date associated with an adverse event, only the treatment-emergence will be imputed using the algorithm described in [Appendix B](#). Dates will not be imputed.

A TEAE is defined as an AE with onset at or after the first dose of IP (SAGE-324). Summary tables of AEs will include TEAEs only and will summarize data using the Safety Set participants overall and by dose level taken immediately prior to the AE onset.

An overall adverse event summary table will be presented for TEAEs and will include the number and percent of participants experiencing at least one:

- TEAE
- Maximum severity of TEAE (mild TEAE, moderate TEAE, severe TEAE)

- TEAE leading to dose interruption
- TEAE leading to dose reduction
- TEAE related to IP
- TEAE leading to IP discontinuation
- TEAE leading to study discontinuation
- Serious TEAE
- Serious TEAE related to IP
- Serious TEAE leading to IP discontinuation
- Serious TEAE leading to study discontinuation
- TEAE resulting in death

The incidence of TEAEs will be summarized by System Organ Class (SOC) and Preferred Term (PT). In addition, summaries will be provided by maximum severity (mild < moderate < severe) and by maximum relationship (related > not related) to IP. Any TEAEs leading to IP discontinuation, any TEAE leading to study discontinuation, and any treatment-emergent SAEs will also be summarized, sorted by descending frequency in SOC and PT.

Participants will be counted only once within each SOC and PT at the maximum severity in the following order: severe, moderate, and mild. Participants will be counted only once within each SOC and PT at the strongest relationship to IP in the following order: related, not related to IP. An AE with missing severity will be considered as 'severe', and with missing relationship to IP will be considered as 'related' for the purposes of summarizing these data.

The incidence of TEAEs and treatment-emergent SAEs will also be presented in order of decreasing frequency by PT.

All AEs (including those with onset before the start of IP) through the end of the study will be listed. In addition, separate listings containing individual participant AE data for all deaths, SAEs, AEs leading to IP discontinuation, and AEs leading to study discontinuation will be provided.

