12.2. Adverse and Serious Adverse Events

12.2.1. Adverse Event Definition

An AE is any untoward medical occurrence in a participant or clinical investigation participant administered a pharmaceutical product and that does not necessarily have a causal relationship with this treatment. An AE can therefore be any unfavorable and unintended sign (including an abnormal laboratory finding), symptom or disease temporally associated with the use of a medicinal (investigational) product whether or not related to the medicinal (investigational) product. In clinical studies, an AE can include an undesirable medical condition occurring at any time, including baseline or washout periods, even if no study treatment has been administered.

A TEAE is defined as an AE with onset after the start of IP, or any worsening of a pre-existing medical condition/AE with onset after the start of IP and throughout the study. The term IP includes any Sage IP, a comparator, or a placebo administered in a clinical study.

Laboratory abnormalities and changes from baseline in vital signs, and ECGs are considered AEs if they result in discontinuation or interruption of study treatment, require therapeutic medical intervention, meet protocol specific criteria (if applicable) or if the investigator considers them to be clinically significant. Any abnormalities that meet the criteria for an SAE should be reported in an expedited manner. Laboratory abnormalities and changes from baseline in vital signs and ECGs that are clearly attributable to another AE do not require discrete reporting (eg, electrolyte disturbances in the context of dehydration, chemistry and hematologic disturbances in the context of sepsis).

All AEs that occur after any participant has signed the informed consent and throughout the duration of the study, whether or not they are related to the study, must be reported to Sage Therapeutics.

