12.2.5. Recording Adverse Events

AE spontaneously reported by the participant and/or in response to an open question from the study personnel or revealed by observation will be recorded during the study at the investigational site. The AE term should be reported in standard medical terminology when possible. For each AE, the investigator will evaluate and report the onset (date and time), resolution (date and time), intensity, causality, action taken, outcome and seriousness (if applicable), and whether or not it caused the participant to discontinue the IP or withdraw from the study.

Intensity will be assessed according to the following scale:

- Mild: symptom(s) barely noticeable to participant or does not make participant uncomfortable; does not influence performance or functioning; prescription drug not ordinarily needed for relief of symptom(s)
- Moderate: symptom(s) of a sufficient severity to make participant uncomfortable; performance of daily activity is influenced; participant is able to continue in study; treatment for symptom(s) may be needed
- Severe: symptom(s) cause severe discomfort; symptoms cause incapacitation or significant impact on participant's daily life; severity may cause cessation of treatment with IP; treatment for symptom(s) may be given and/or participant hospitalized

It is important to distinguish between serious and severe AEs. Severity is a measure of intensity whereas seriousness is defined by the criteria under Section 12.2.2. An AE of severe intensity may not necessarily be considered serious.

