13.7.1. Adverse Events

AEs will be coded using Medical Dictionary for Regulatory Activities (MedDRA) Version 23.1 or higher. A TEAE is defined as an AE with onset after the first dose of IP. The analysis of AEs will be based on the concept of TEAEs. The incidence of TEAEs will be summarized by System Organ Class and Preferred Term. In addition, summaries will be provided by intensity (mild, moderate, severe) and by causality (related, not related) to IP.

Any TEAEs leading to discontinuation of treatment or withdrawal from the study and any treatment-emergent SAEs will be summarized.

All AEs and SAEs (including those with onset or worsening before the start of IP) through the end of the study will be listed.

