8. STATISTICAL ANALYSIS

8.1. General Considerations

All participant data, including those that are derived, that support the tables and figures will be presented in the participant data listings. Some data may be presented only in participant data listings, some may be presented with a corresponding table or figure; these will be indicated in relevant sections below.

For all safety [REDACTED] analyses where applicable, baseline is defined as the last non-missing measurement prior to the first dose of IP. For scores that are made up of item scores, all item scores must come from the same visit to be considered as baseline for the overall score.

Continuous endpoints will be summarized with n, mean, standard deviation (SD), median, first and third quartiles (Q1, Q3), minimum (min), and maximum (max). The minimum and maximum will be reported with the same number of decimal places as the source (raw) data. Mean and median will be reported to 1 decimal place more than the source (raw) data and standard deviation will be reported to 2 decimal places more than the source (raw) data. Any values that require transformation to standard units (metric or SI) will be converted with the appropriate corresponding precision. In addition, change from baseline values will be calculated at each time point and summarized descriptively.

Categorical endpoints (eg, incidence of an adverse event) will be summarized using counts and percentages. Percentages will be presented to 1 decimal place unless otherwise specified.

Participants will be summarized according to treatment received. “By-visit” summaries are based on the last dose received before the specific evaluation. Adverse events summaries are based on the last dose received before the start of the AE. Note that it is possible for a participant to be counted under more than one dose in summaries. Since baseline is by definition before the first dose of IP, baseline values in listing will have no dose designation, and in summaries it will be presented under “Sage-324 Overall”. For displays for which no such date applies, e.g. demographics, disease history, etc., the presentation will not be by dose group, but will be by aggregate SAGE-324 group.

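### The primary endpoint has two definitions: Protocol 12.2.1 counts on-drug worsening as a TEAE, but Protocol 13.7.1 and SAP 8.4.1 count onset only, so some worsening may be missing from every TEAE table

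*SAP*

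**What the plan says.** SAP 4.1 makes the incidence of TEAEs the primary endpoint. Three sections define a TEAE.

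- **Protocol 12.2.1** counts an AE that begins after the start of IP, "or any worsening of a pre-existing medical condition/AE with onset after the start of IP and throughout the study".
- **Protocol 13.7.1** counts onset only: "A TEAE is defined as an AE with onset after the first dose of IP".
- **SAP 8.4.1** also counts onset only, with a slightly different boundary: "A TEAE is defined as an AE with onset at or after the first dose of IP (SAGE-324").

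The listing sentences differ as well. Protocol 13.7.1 lists all AEs, "including those with onset or worsening before the start of IP". The SAP version drops the reference to worsening: "All AEs (including those with onset before the start of IP) through the end of the study will be listed".

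Four other provisions matter:

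- SAP 8.4.1 restricts the tables: "Summary tables of AEs will include TEAEs only".
- SAP 8.1 assigns dose level by AE start: "Adverse events summaries are based on the last dose received before the start of the AE".
- SAP Appendix B classifies AEs with partial dates from start and end dates and has no test for worsening.
- Protocol 12.2.5 sets what is recorded: "For each AE, the investigator will evaluate and report the onset (date and time), resolution (date and time), intensity", among other items. It does not say whether a worsening opens a new record.

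SAP 6.1 declares no departure from the protocol's analyses.

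**The concern.** Two readers who follow different sections would classify the same record differently, and the record feeds the primary endpoint. AEs are collected from consent (Protocol 12.2.1) and Screening can last 28 days, so a participant can reach Day 1 with an AE already open. If that AE worsens on SAGE-324 and stays under its original onset date, the SAP rule does not count it.

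The event would then be missing from overall incidence and from the severity, relatedness, serious and discontinuation summaries (Tables 14.3.1.1 to 14.3.1.9 in SAP Appendix C). Disposition by primary reason, ESS change, and laboratory or ECG shifts might show part of it, but not as an AE. The study has one open-label arm, so an undercount is not offset by a similar undercount in a control group.

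The rule also sits oddly with the SAP's other conventions. Missing severity is treated as severe and missing relationship as related. An AE with no start date is a TEAE if it ends on or after the first dose. An undated event is therefore counted, while a fully dated event known to have worsened on drug is not.

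**Working it through.** The plan gives no figure to reproduce. The sample size of about 750 is tied to ICH E1A exposure and has no statistical inputs. The check is therefore a comparison of the rules, followed by an illustration of size.

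**Rules applied to one case.** An AE starts in Screening as mild, is still present on Day 1, becomes severe after dosing, and is kept as one record.

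| Rule | Result |
|---|---|
| Protocol 12.2.1 | TEAE (worsening limb) |
| Protocol 13.7.1 | Not a TEAE (onset before first dose) |
| SAP 8.4.1 | Not a TEAE (onset before first dose) |
| SAP Appendix B, if the start date is partial but its year, or year and month, precedes the first dose | Not a TEAE, even if the AE continues on drug |
| SAP 8.1 dose attribution | No dose level, because no dose precedes the AE start |
| SAP 8.4.1 tables | Absent |
| SAP 8.4.1 listings | Present |

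If the site instead closes the first record and opens a new one on the day of worsening, the new record starts after dosing and all three definitions count it. The loss therefore depends on a recording convention that neither document states.

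Conditions held only as medical history are outside this pool. Their worsening would be entered as an AE that begins after dosing, and it would be counted.

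**Size, with assumed inputs.** Only N = 750 comes from the documents. The other four inputs are assumptions:

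- a = 0.01 to 0.10: share of participants with an AE that began between consent and Day 1 and is ongoing
- b = 0.05 to 0.20: share of those whose AE worsens on drug
- c = 0 to 1: share of worsenings kept under the old record
- d = 0.05 to 0.30: share of affected participants with no other TEAE

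Participants with an omitted worsening = 750 × a × b × c.

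- Minimum (c = 0): 0
- Low a and b, c = 1: 750 × 0.01 × 0.05 = 0.4
- Mid case (a = 0.05, b = 0.10, c = 0.5): 750 × 0.05 × 0.10 × 0.5 = 1.9
- Maximum (c = 1): 750 × 0.10 × 0.20 = 15, and 15 / 750 = 2.0%

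Change in participants with at least one TEAE = omitted × d.

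- Mid case: 1.9 × 0.05 = 0.1 to 1.9 × 0.30 = 0.6 participants, under 0.1 percentage point
- Maximum: 15 × 0.30 = 4.5 participants, and 4.5 / 750 = 0.6 percentage points

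Within these ranges one Preferred Term could change by at most 2.0 points, and only if all 15 events fell in that term. The 15 is a ceiling for these inputs, not a bound in general. If 5% of 750 had such an event, about 38 participants would be affected.

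**The case against.** The strongest reply is that nothing may be lost in practice. No passage says a worsening stays under the old record, and case report form instructions, where the convention would normally sit, are not among the documents. The text can be read as favouring separate records: 12.2.1 speaks of a worsening with its own onset, 13.7.1 treats worsening as something that can be dated, and 12.2.5 describes one onset and one intensity per AE. On that reading the onset-only wording is shorthand. This is a fair limit on the consequence, and it is why the effect may be zero. It does not remove the conflict, because the SAP as written does not depend on that reading or state it.

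The effect is also small in the mid case, the inputs are assumed, and the study is descriptive with no hypothesis test. All of that stands.

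The separate listings of deaths, SAEs and AEs leading to discontinuation are not restricted to TEAEs, so the gravest worsenings would be visible one by one. That is a real safeguard, but it does not put them into the incidence tables.

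Finally, SAP 6.1 agrees with 13.7.1 on worsening, so its statement is not false on this point. It simply leaves the difference from 12.2.1 unmentioned.

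**Conclusion.** The concern holds. The protocol defines its primary endpoint in two ways, and the SAP adopts the narrower one without saying so. As written, it can drop on-drug worsening of a screening-period AE from every TEAE table. This particular omission can only lower the count. The separate change from after to at or after the first dose works, if at all, in the other direction.

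Confidence is high that the definitions conflict. How many events are affected is unknown and depends on how sites record worsening. The illustrative effect is modest, but the conflict bears on the primary endpoint and should be resolved before database lock.

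**What to change.** Use one definition in SAP 8.4.1 and Protocol 13.7.1 that agrees with 12.2.1 on worsening: *an AE that begins at or after the first dose of SAGE-324 in 324-ETD-303, or a condition or AE already present that gets worse after that dose.* Settle the boundary (after, or at or after) in all three sections. Naming the study matters because 12.2.1 lets IP mean any Sage product given in a clinical study, and participants enter from another SAGE-324 study.

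Then:

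- Use the date of worsening as the onset date for treatment-emergence and for dose level. State that a worsening is entered as a new AE.
- For data already collected, review before lock the AEs that began before the first dose and either ended on or after it or are ongoing.
- Extend Appendix B to partial dates of worsening.
- Restore the reference to worsening in the SAP listing sentence, and state the alignment in SAP 6.1.

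If the sponsor prefers onset-only, 12.2.1 still has to be reconciled and the choice declared in SAP 6.1.

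The cost is a wording change in two sections, small consequential edits to Appendix B and SAP 6.1, and review of what should be a limited set of records. Protocol 12.2.5 describes no date of worsening, so some records may need site queries, and a site instruction alone would not repair them. The protocol change must also go through the IRB (Protocol 16.1). Reported incidence may rise slightly.

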8.4.2. Clinical Laboratory

All statistical analyses of laboratory values will be performed using SI units. The following parameters are mentioned in the protocol, hence will be summarized; any other parameters for which data are reported will be listed but not summarized.

Biochemistry:

- Renal Panel: glucose, calcium, phosphorus, blood urea nitrogen, creatinine, sodium, potassium, chloride, total carbon dioxide content
- Hepatic Panel: albumin, alanine transaminase (ALT), aspartate transaminase (AST), total bilirubin, direct bilirubin, indirect bilirubin, alkaline phosphatase, total protein, lactate dehydrogenase, gamma glutamyl transferase, creatine kinase (MB and MM)

- Other: total lipid profile, creatine phosphokinase, thyroid stimulating hormone (TSH), alcohol level, HbA1c

Coagulation:

- Activated partial thromboplastin time, prothrombin time, and international normalized ratio

Hematology:

- Red blood cell (RBC) count, hemoglobin, hematocrit, white blood cell count with differential, platelet count, and if RBC indices are abnormal, reflex RBC morphology is indicated

Urinalysis:

- Protein, glucose, pH, blood, leukocytes, leukocyte esterase, urobilinogen, bilirubin, ketones, nitrite, myoglobin

Some numeric lab values may be reported as ‘<n.n’ or ‘>n.n’; these will be analyzed in the summary statistics as n.n/2 and n.n, respectively. For example, triglycerides recorded as “<0.50” mmol/L would be analyzed as 0.25 mmol/L and potassium recorded as “>6.0 mmol/L” would be analyzed as 6.0 mmol/L.

All by-visit laboratory summary tables will present results for the Safety Set participants overall, and by dose level received prior to the given evaluation. For summarization of incidence data any time post-baseline, participant data will be summarized according to the last dose received when a particular criterion was met (thus, a participant may contribute data under more than one dose if a criterion was met post-baseline while taking different doses).

Continuous hematology, chemistry, coagulation, and urinalysis results (raw and change from baseline) will be summarized at each scheduled time point. Categorical urinalysis results will be summarized by frequencies and percentages at each scheduled time point. The number and percentage of participants with shift from baseline based on the laboratory normal ranges provided by the laboratory will be tabulated at each scheduled visit.

Any laboratory value considered clinically significant by the investigator is captured as an adverse event.

The number and percentage of participants with potentially clinically significant (PCS) values at any time after IP administration (including unscheduled visits) will be summarized for the hematology, chemistry, and coagulation parameters defined in [Table 5](#), [Table 6](#), and [Table 7](#), respectively. PCS values for each scheduled visit and end-of-treatment and end-of-study values will also be provided. These summaries will be done using the Safety Set, overall for SAGE-324 as well as by dose level.

Liver function tests will be monitored closely; PCS values ([Table 8](#)) will be summarized using the Safety Set for incidence any time post-baseline for these PCS thresholds (for conditions involving more than one parameter, the results need to be from the same timepoint).

Chemistry, hematology, coagulation, and urinalysis data will be listed with the values outside the normal ranges and PCS criterion flagged. Blood cell morphology and microscopy test results will be listed when available but not summarized. Virus serology, pregnancy tests, and urine drugs of abuse data will be listed but not summarized.

Table 5: Potentially Clinically Significant Values for Hematology

Laboratory Parameter	Sex	Units	Criteria for PCS Values (Observed values)	
			High	Low
Hemoglobin	Male	g/L	>185	<115
	Female	g/L	>170	<100
Hematocrit	Male	Fraction of 1	>0.55	<0.385
	Female	Fraction of 1	>0.49	<0.345
Platelet count		10 ⁹ /L	>600	<125
White blood cell		10 ⁹ /L	>15	<2.5
Basophils		10 ⁹ /L	>0.5	NA
Eosinophils		10 ⁹ /L	>1.5	NA
Neutrophils		10 ⁹ /L	NA	<1.5
Lymphocytes		10 ⁹ /L	>6.0	<0.5
Monocytes		10 ⁹ /L	>1.4	NA

Table 6: Potentially Clinically Significant Values for Chemistry

Laboratory Parameter	Units	Criteria for PCS Values (Observed values)	
		High	Low
Albumin	g/L	>70	<28
Blood urea nitrogen	mmol/L	>10.71	NA
Calcium	mmol/L	>2.75	<2.0
Chloride	mmol/L	>120	<90
Creatinine	mmol/L	>3xULN or >3x Baseline	
Gamma Glutamyl Transferase		>3xULN	
Glucose	mmol/L	>13.9	<2.8
Sodium	mmol/L	>150	<132
Potassium	mmol/L	>5.4	<3.3
Protein	g/L		<45
Bicarbonate	mmol/L	>34	<18
Chloride	mmol/L	>120	<90
Phosphorus	mmol/L	>1.94	<0.61
Liver Function Tests (LFT)			
Bilirubin	μmol/L	>2xULN	
Aspartate Aminotransferase	U/L	>3xULN	
Alanine Aminotransferase	U/L	>3xULN	
Alkaline Phosphatase	U/L	>1.5xULN	

Table 7: Potentially Clinically Significant Values for Coagulation

Parameter	Potentially Clinically Significant Values
Prothrombin time (PT)	>=1.11 x ULN
Activated partial thromboplastin time (aPTT)	>1.5 x ULN

Table 8: Potentially Clinically Significant Values for Liver Function Tests

Parameter	Potentially Clinically Significant Values
Alanine Aminotransferase	>3xULN, >5xULN, >10xULN
Aspartate Aminotransferase	>3xULN, >5xULN, >10xULN
Alanine Aminotransferase OR Aspartate Aminotransferase	>3xULN, >5xULN, >10xULN
Alkaline Phosphatase	>1.5xULN, >2xULN
Total Bilirubin	>1.5xULN, >2xULN
Total Bilirubin > 2xULN AND (Alanine Aminotransferase OR Aspartate Aminotransferase >3xULN), any time postbaseline, do not need to be at the same visit	
Potential Hy's Law: [Total Bilirubin >=2xULN AND Alkaline Phosphatase <2xULN, measured at the same visit] AND [(Alanine Aminotransferase OR Aspartate Aminotransferase >3xULN) AND Alkaline Phosphatase <2xULN, measured at the same visit], two conditions at any time postbaseline, do not need to be at the same visit	

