9. Participant is willing to limit use of alcohol to 2 units per day for males and 1 unit per day for females starting at least 1 week prior to Day 1 and through the EOS Visit.
A unit of alcohol is defined as: 12 ounces of regular beer, 5 ounces of wine, or 1.5 ounces of distilled spirits.
Participant will limit alcohol use to at least 2 hours before self-administration of IP in the evening.
Participant will not use alcohol starting 24 hours prior to scheduled in-clinic study visits until all assessments have been completed.
10. Participant is willing to maintain prestudy consumption of products that contain nicotine starting at least 1 week prior to Day 1 and through EOS Visit.

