- ^b Vital signs comprise heart rate, respiratory rate, temperature, and blood pressure. Systolic and diastolic blood pressure are to be measured after the participant has been supine for at least 5 minutes prior to the measurement. Orthostatic blood pressure and heart rate will also be measured after the participant has been in the supine position for at least 5 minutes and then repeated approximately 1 and 3 minutes after standing. On Day 1, supine and standing blood pressure and heart rate will be collected in triplicate at least 15 minutes apart, measured after the participant has been in the supine position for at least 5 minutes and then repeated 1 minute and 3 minutes after standing. Respiratory rate and temperature are collected once on Day 1.
- ^c ECGs will be collected and read locally. All ECGs must be performed after the participant has been in a supine position for at least 5 minutes.
- ^d Chemistry, hematology, coagulation, and urinalysis at Screening and at all additional timepoints. Myoglobin (urinalysis) and serum creatine kinase (biochemistry) at Screening and at additional timepoints at the discretion of the investigator. A serum sample for blood alcohol level will be collected at Screening and all additional timepoints. HbA1c will be collected at Screening.
- At the discretion of the investigator, clinical laboratory assessments from another SAGE-324 study may be used to determine eligibility for this study if within 28 days of Day 1.

^g Participants will be trained by study personnel on the use of software applications, IP diary, and devices necessary for the conduct of the study.

^h Participants will self-administer orally 15 mg SAGE-324 on Day 1 to Day 14, 30 mg on Day 15 to Day 28, 45 mg on Day 29 to Day 42, and then 60 mg daily starting on Day 43. If a participant experiences AEs that are considered at any time in the Treatment Period by the investigator to be related to the IP and not tolerable, the investigator may reduce the dose of IP in 15 mg decrements, including during the initial dose escalation period. Self-administration of IP will be interrupted for 3 to 8 days before the initiation of the reduced dose.

ⁱ Participants will self-administer orally on an outpatient basis a single dose of SAGE-324 once daily in the evening before bed, with a snack if bedtime is not within 2 hours of the evening meal.

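### SAP 8.4.2 halves every below-limit laboratory result without restricting this to concentrations with a limit near zero; if urine pH, coagulation, HbA1c or alcohol results arrive in that form, their descriptive summaries are distorted or uninformative

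*SAP*

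**What the plan says.** SAP 8.4.2 names the parameters that will be summarized. Among them are "thyroid stimulating hormone (TSH), alcohol level, HbA1c" under biochemistry, "Activated partial thromboplastin time, prothrombin time, and international normalized ratio" under coagulation, and urine pH in the urinalysis list ("Protein, glucose, pH, blood, leukocytes, leukocyte esterase, urobilinogen, bilirubin, ketones, nitrite, myoglobin").

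The substitution rule follows directly. It opens with "Some numeric lab values may be reported as" '<n.n' or '>n.n', and continues: "these will be analyzed in the summary statistics as n.n/2 and n.n, respectively". The SAP's illustration is triglycerides below 0.50 mmol/L, which "would be analyzed as 0.25 mmol/L and potassium recorded as" above 6.0 is kept at 6.0. No analyte is exempted.

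Continuous results and their changes from baseline are then summarized at each scheduled time point. Under SAP 8.1 the statistics are n, mean, SD, median, quartiles, minimum and maximum. Change from baseline in laboratory parameters is a secondary endpoint (SAP 4.2).

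On alcohol, the laboratory footnote in SAP Appendix A states: "A serum sample for blood alcohol level will be collected at Screening and all additional timepoints". Inclusion criterion 9 (Protocol 8.1) states: "Participant will not use alcohol starting 24 hours prior to scheduled in-clinic study visits until all assessments have been completed".

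**The concern.** Replacing a censored value by half its limit is a common convention for a concentration whose true value may lie anywhere between zero and a small limit. It has no such basis for pH, which is a logarithmic scale, or for INR, clotting times and HbA1c, whose values do not run down towards zero. For these, half the limit falls far below any value the censored result is likely to represent. One such result sets the printed minimum, and a modest fraction moves the mean and widens the SD. A participant who crosses the limit between baseline and a visit shows a large artificial change.

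Alcohol raises a different problem. Halving is conventional for it, but most results should be undetectable because of the 24-hour rule. If those results are reported as '<L', the by-visit median is L/2, which reflects the assay and not the participants. What a reader needs is how many participants had detectable alcohol. The laboratory analyses in SAP 8.4.2 and the visible list of displays contain no count designed for that.

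**Working it through.** **The SAP's own example.** 0.50 / 2 = 0.25 mmol/L, and '>6.0' stays 6.0. Both match the SAP.

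**Single values.** The limits below are assumed; the documents give none.
- Urine pH: '<4.5', '<5.0' and '<5.5' become 2.25, 2.5 and 2.75. On the log scale, moving from 5.0 to 2.5 implies a 10^2.5 = 316-fold higher hydrogen ion concentration.
- INR: '<0.8', '<0.9' and '<1.0' become 0.40, 0.45 and 0.50.
- Change from baseline: pH from 5.5 to '<5.0' is analysed as 2.5 − 5.5 = −3.0; using the limit it would be 5.0 − 5.5 = −0.5.

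**Effect on mean and SD.** Inputs, all assumed: pH mean 6.0, SD 0.7; INR mean 1.02, SD 0.08; values below the limit L are censored, so the censored fraction follows from the distribution.

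With z = (L − μ)/σ:
- censored fraction p = Φ(z)
- λ = φ(z)/(1 − p)
- observed part: mean m₁ = μ + σλ, variance v₁ = σ²(1 + zλ − λ²)
- with substituted value s: mean m = (1 − p)m₁ + ps; variance = (1 − p)[v₁ + (m₁ − m)²] + p(s − m)²

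Worked case, pH with L = 5.0:
- z = −1.429, p = 0.0766, λ = 0.1557, m₁ = 6.109, v₁ = 0.369
- s = 5.0: mean 6.02, SD 0.654
- s = 2.5: mean 5.83, SD 1.123
- SD ratio 1.123 / 0.654 = 1.72; mean shift −0.0766 × 2.5 = −0.19

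| Analyte, limit | Censored | Mean, SD using limit | Mean, SD using half | SD ratio | Mean shift |
|---|---|---|---|---|---|
| pH, 5.0 | 7.7% | 6.02, 0.654 | 5.83, 1.123 | 1.7 | −0.19 |
| pH, 4.5 | 1.6% | 6.00, 0.690 | 5.97, 0.815 | 1.2 | −0.04 |
| INR, 0.9 | 6.7% | 1.022, 0.075 | 0.992, 0.160 | 2.1 | −0.03 |
| INR, 0.8 | 0.3% | 1.020, 0.080 | 1.019, 0.086 | 1.1 | −0.001 |

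Using the limit leaves the mean within 0.024 (pH) and 0.002 (INR) of the assumed true mean.

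**Alcohol.** Assume a limit L and that more than half of participants are below it and reported as '<L'. The median is then L/2: for L = 0.5, 1.0, 2.2 and 5.0 mmol/L, it is 0.25, 0.5, 1.1 and 2.5 mmol/L. If every result is below the limit, the mean is also L/2 and the SD is 0. If baseline and visit are censored at the same limit, the change is L/2 − L/2 = 0. If the laboratory reports 0 or 'negative', the rule is not triggered.

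**Flags for potentially clinically significant values.** SAP Table 7 sets only high-side limits for prothrombin time and aPTT. Tables 5 to 8 contain no criterion for INR, urine pH, alcohol or HbA1c. A halved low value can neither create nor hide a flag.

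**The case against.** The strongest reply is that nothing may happen. The rule acts only on results that carry '<', and the documents neither say that these analytes will be reported that way nor give a limit for any of them. Nor do they say whether urine pH is summarized as a continuous or a categorical urinalysis parameter. This stands, and it makes the point conditional. It does not repair the rule, which as written gives an unsuitable value whenever the condition is met.

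Four stronger readings are tempting, and the documents do not support them:
- That the plan produces impossible values. The substituted figures are implausible as measurements, but they arise only under assumed limits.
- That mean alcohol is fixed at half the limit whatever participants drink. Any detectable result raises the mean; only the median stays at L/2, and only while most results are censored.
- That detectable alcohol is lost. It appears in the maximum and the listings, and possibly in the shift table if the laboratory supplies a reference range. Alcohol use is also collected separately to check inclusion criterion 9 (Protocol Table 2, footnote k).
- That keeping n.n for '>n.n' makes the rule inconsistent. An upper-censored value has no finite midpoint, so the asymmetry is not itself an error.

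It is also fair to say that substituting the limit is a crude method with a slight upward bias. In the cases above that bias is much smaller than the downward bias from halving.

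**Conclusion.** The point holds as a small, conditional defect in a stated rule. SAP 8.4.2 applies halving to analytes for which it is unsuitable. If urine pH, INR, prothrombin time, aPTT or HbA1c results are reported as '<n.n', the minimum, mean, SD and change from baseline are distorted. For pH and INR the SD inflation is about 1.1 to 2.1 fold over the assumed limits, and the mean shift is at most −0.19 and −0.03. These sizes rest on assumed means, SDs, limits and normality; prothrombin time, aPTT and HbA1c were not quantified. For alcohol, the by-visit median would be uninformative, while change from baseline is unaffected when both values are censored at the same limit. The consequences are confined to descriptive safety summaries: no hypothesis test is involved and no flag for potentially clinically significant values changes.

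**What to change.** Amend the substitution sentence in SAP 8.4.2 in two respects:
- Restrict n.n/2 to concentrations with a quantitation limit near zero.
- Analyse '<n.n' as n.n for urine pH, INR, prothrombin time, aPTT and HbA1c.

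Add the number and percentage of participants with detectable alcohol, by visit and at any time after baseline.

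The cost is one sentence and one small table, with no new data. The price in accuracy is the slight upward bias from using the limit, which a table footnote can state.
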